#### 2.1.4 Ending randomisation to Regimen A

According to Version 7.0 of the Stage 2 protocol, patients may be randomised to Regimen A unless the participating country has adopted or has imminent plans to adopt a short MDR-TB regimen, in keeping with the WHO 2016 guidelines. This is because patients eligible for STREAM would also meet the WHO criteria for a shortened regimen and it is very unlikely that patients would accept the possibility of randomisation to a 20- to 24-month treatment regimen when under routine care they would be treated with a 9-month regimen. In addition, patients already enrolled in the trial and allocated to Regimen A would be more likely to subsequently withdraw from the trial, thus reducing the scientific value of the results.

With Version 8.0 of the protocol, randomisation to Regimen A will cease completely because several of the countries participating in STREAM have already implemented or have plans to implement a shortened regimen. As a result Regimen A would not have sufficient concurrently randomised patients for comparison and therefore continuation is considered futile. In addition, Stage 1 of

\* Following implementation of protocol Version 8.0 recruitment to Regimen A and Regimen D was discontinued and in Regimen B moxifloxacin was replaced by levofloxacin. Following implementation of protocol version 10.0, either kanamycin or amikacin will be used in Regimen B, depending on availability.

STREAM provides a good estimate of the performance of Regimen A under trial conditions. Patients already enrolled and allocated to Regimen A will continue on that treatment.

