#### **Unfavourable**

A patient's outcome will be classified as **unfavourable** if:

- They are discontinued from their allocated study treatment and subsequently restarted on a different MDR-TB regimen.
- 2. Treatment is extended beyond the scheduled end of treatment for any reason other than making up days when no treatment was given (missed treatment) for a maximum of eight weeks. A maximum of 14 days of extra treatment (irrespective of reason) is acceptable before it is classified as treatment extension. In addition, if the intensive phase of treatment has been extended for delayed sputum conversion (maximum 8-week extension permitted) the scheduled end of treatment will also be extended by the same amount, in accordance with Section 7.3.2.
- 3. They are restarted on any MDR-TB treatment after the scheduled end of treatment, but before 132 weeks after randomisation for Stage 1 and before 76 weeks after randomisation for Stage 2.
- 4. They change their allocated study treatment for any reason other than (1) the replacement of a single drug\* or (2) for patients allocated to Regimen A when the change is as a result of changes in local guidelines and not related to any change in the patient's circumstances or condition.
- 5. Bedaquiline is started where the allocated regimen did not originally contain that drug (Regimen A or B)
- 6. A second line injectable agent is started in Regimen C.
- 7. A drug from the class of nitroimidazoles or linezolid is started.
- 8. They die at any point during treatment or follow-up.
- 9. At least one of their last two culture results, from specimens taken on separate occasions, is positive.
- 10. They do not have a culture result at Week 76 or thereafter for the Stage 1 comparison, or within the Week 76 window for the Stage 2 comparison.

11. The failure or recurrence specimen at or before the Week 76 window was a different strain to their randomisation specimen, i.e. re-infection (the Stage 2 comparison only).

Starting a single drug is not considered to be a substantial change to the regimen and therefore does not result in an unfavourable outcome, with the exception of adding bedaquiline (in Regimen A or B), a second-line injectable in Regimen C or a drug from the class of nitroimidazoles or linezolid (in any regimen).

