Following publication of the revised WHO guidelines in 2018 it became more likely that a salvage regimen following bedaquiline use would contain linezolid rather than an injectable agent. To reflect the resulting imbalance in the likelihood of point 5 and 6 occurring based on drug choice, starting linezolid alone was added as an unfavourable outcome (point 7 above) in version 11.0.

For analysis of the Stage 1 comparison, re-infections with a different strain are classified as not assessable.

Only data before or within the Week 76 window will be used for the determination of the primary efficacy outcome for Stage 2, even though patient follow-up continues to end of trial. Participants with no sputum sample available at Week 76 due to Covid-19 who are not otherwise classified as unfavourable will be considered unfavourable in line with the above definition. Sensitivity analyses will reclassify these participants as i) **non-assessable** and excluded from the primary efficacy analysis, and ii) unfavourable/favourable if their culture result at their Week 68 visit is positive/negative respectively.

An extension of the intensive phase of treatment in any study arm does not constitute an unfavourable outcome, as long as the extension is in accordance with either the algorithms described in Figures 9 and 10 (section 7.3.2) for patients on Regimen B, Regimen C, or Regimen D, or the locally-used WHO 2011 long MDR-TB regimen for patients on Regimen A. Similarly, the discontinuation of drugs that are not replaced does not constitute an unfavourable outcome.

During Stage 1, a patient who has a culture result within the Week 76, but not within the Week 132 window having not otherwise been classified as unfavourable (based on the definitions above) will be regarded as **not assessable** and will be excluded from the primary analysis provided their last two cultures, from specimens taken on separate occasions, are negative; one of these cultures should be from a sample taken at week 76. Any patient who does not have a culture result within the Week 132 window and does not fulfil these criteria will be classified as **unfavourable**. These definitions apply to both Regimen A and Regimen B in Stage 1 of the trial.

### 11.2.2 Secondary efficacy outcome at Week 132 in Stage 2

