- 1. They are discontinued from their allocated study treatment and subsequently restarted on a different MDR-TB regimen.
- 2. Treatment is extended beyond the scheduled end of treatment for any reason other than making up days when no treatment was given (missed treatment) for a maximum of eight weeks. A maximum of 14 days of extra treatment (irrespective of reason) is acceptable before it is classified as treatment extension.
- 3. They are restarted on any MDR-TB treatment after the scheduled end of treatment, but before 76 weeks after randomisation.
- 4. They change their allocated study treatment for any reason other than the replacement of a single drug.
- 5. Bedaquiline is started where the allocated regimen did not originally contain that drug (Regimen A or B).
- 6. A second line injectable agent is started in Regimen C.
- 7. A drug from the class of nitroimidazoles (delamanid or pretomanid) or linezolid is started.
- 8. They die at any point during treatment or follow-up.
- 9. At least one of their last two culture results, from specimens taken on separate occasions, is positive.
- 10. They do not have a culture result within the Week 76 window.

Starting a single drug other than bedaquiline (in Regimen A or B) or from the class of nitroimidazoles (delamanid or pretomanid) or linezolid (in any regimen) is not considered to be a substantial change to the regimen and therefore does not result in an unfavourable outcome, providing none of the other criteria above are met.

An extension of the intensive phase of treatment in any study arm does not constitute an unfavourable outcome, as long as the extension is in accordance with the algorithms described in Figure 5 and Figure 6 in Section 1.5 for patients on Regimen B, Regimen C, and Regimen D. Similarly, the discontinuation of drugs that are not replaced does not constitute an unfavourable outcome.

These definitions of favourable and unfavourable apply to all four treatment regimens and for analyses of both the mITT, PP and mPP analysis populations.

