The assumption of proportional hazards between the two comparisons will be tested using the proportional hazards test based on the Schoenfeld residuals after fitting the Cox Proportional Hazards models. In the case where there is adequate evidence that the proportional hazard assumptions are violated at the 5% level (i.e. p<0.05), methods where proportional hazards is not a necessary assumption will be used, such as the Wilcoxon test of equality of survivor functions and restricted mean survival time.

Sensitivity analyses will be conducted i) considering different dichotomies of the 5 point scale and ii) assessing the assumption of independent or non-informative censoring (i.e. that the likelihood of an FoR event at the time of censoring is assumed to be the same as for those in whom no censoring occurred) using inverse probability of censoring weights (IPCW)⁸ and multiple imputation(MI)⁹ respectively.

This failure or recurrence analysis will be repeated in subgroups according to baseline characteristics as described in Section 6.3.

7.1.4 Favourable outcome at Week 132

A patient's outcome will be classified as favourable if their last two sputum culture results are negative, unless they have previously been classified as unfavourable. These two sputum results must be from samples taken at separate visits; the latest must be no more than six weeks before their scheduled last efficacy visit (see Section 7.1).

A patient's outcome at their scheduled last efficacy visit will be classified as unfavourable if:

- They are unfavourable at Week 76
- They start any MDR-TB treatment between their Week 76 and scheduled last efficacy visits
- They die between their Week 76 and scheduled last efficacy visits
- At least one of their last two culture results, from specimens taken on separate occasions, is positive.

A patient who does not have a culture result within the window for their scheduled last efficacy visit, having not otherwise been classified as unfavourable, will be regarded as non-assessable if their last two cultures, from specimens taken on separate occasions, are negative. All other patients who do not have a culture result within the window for their scheduled last efficacy visit and do not meet this definition of non-assessable will be classified as unfavourable.

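### SAP 3.2 item 4 omits the protocol's exemption for guideline-driven changes to Regimen A, which can bias the secondary Week 132 comparisons against A

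*SAP*

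**What the plan says.** - **SAP 3.2, Unfavourable, item 4:** a patient is unfavourable if "They change their allocated study treatment for any reason other than the replacement of a single drug". No other exemption is given.
- **SAP 3.2, closing sentence:** "These definitions of favourable and unfavourable apply to all four treatment regimens". Item 5 also names Regimen A, so A is clearly within the list.
- **Protocol 11.2.1, Unfavourable, item 4:** the single-drug exemption, plus a second one "for patients allocated to Regimen A when the change is as a result of changes in local guidelines and not related to any change" on the patient's side.
- **Precedence:** SAP General Information states that the SAP supersedes the analysis plan in the protocol.
- **Week 132:** SAP 7.1.4 makes anyone unfavourable at Week 76 unfavourable at the scheduled last efficacy visit. It then repeats the analysis for B and A, C and A, and D and A (SAP secondary objectives 8 to 10).

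Two neighbouring texts also bear on Regimen A.

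- **Intensive-phase extension:** Protocol 11.2.1 accepts an extension that follows the algorithms for B, C and D, "or the locally-used WHO 2011 long MDR-TB regimen for patients on Regimen A". SAP 3.2 accepts one "in accordance with the algorithms described in Figure 5 and Figure 6 in Section 1.5 for patients on Regimen B", C or D, and has no Regimen A clause.
- **After Week 76:** SAP 7.1.4 counts a patient as unfavourable if "They start any MDR-TB treatment between their Week 76 and scheduled last efficacy visits". Protocol 11.2.2 uses the same words.

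**The concern.** Regimen A is whatever long regimen is used locally, with drugs supplied by the participating countries (Protocol 7.2.3), so its composition can change by national decision. Regimens B, C and D are defined by the trial, and B was modified only through protocol versions 8.0 and 10.0. Item 4 of the SAP reads the same for every arm, but A is the arm exposed to changes that nobody in the trial chose. The protocol's second exemption dealt with that.

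The protocol foresaw guideline change while patients were in the trial: national adoption of the 2016 guidelines during 2018 (1.1.4) and revised WHO guidance in December 2018 (2.1.1). Without the exemption, a culture-negative patient on A could be scored as a failure for an administrative reason. Protocol 2.2.1 expects Stage 2 data to sharpen the comparison of B with A, and in the protocol the exemption applies to A in both stages.

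**Working it through.** The plan states no figure that depends on this point, so the check is a comparison of texts followed by simple arithmetic.

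**1. Which changes are scored differently?** Consider a guideline-driven change on Regimen A by Week 76, unrelated to the patient:

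| Change on A | Protocol 11.2.1 | SAP 3.2 |
|---|---|---|
| One drug replaced, not by bedaquiline, a nitroimidazole or linezolid | Not unfavourable | Not unfavourable |
| Two or more drugs changed, not meeting items 1, 5 or 7 | Not unfavourable (second exemption) | Unfavourable (item 4) |
| A discontinued and a different regimen started | Unfavourable (item 1) | Unfavourable (item 1) |
| Bedaquiline, a nitroimidazole or linezolid started | Unfavourable (items 5, 7) | Unfavourable (items 5, 7) |

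Only the second row differs.

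**2. Does it reach a reported result?** Yes. Week 76 status carries into the Week 132 outcome, which feeds the three comparisons with A. SAP 1.6 restricts these to participants randomised under protocol v6.2.

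**3. Size per patient.** Protocol 11.4.3 expects no more than 50 patients on A. If k patients out of n are reclassified, the favourable proportion on A falls by 100 × k/n points. The documents give no value for k, so these are illustrations:

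- n = 50: k = 1, 2, 3 gives 2, 4, 6 points.
- n = 25 (assumed): k = 1, 2, 3 gives 4, 8, 12 points.

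This is the shift in a crude proportion. The main Week 132 analysis averages stratum-specific survival curves, so there it is an approximation.

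**4. Size against sampling error.** Assume the Stage 1 proportions (A 79.8%, B 78.8%; Protocol 2.1.1), 50 on A, and 100 on B from the 1:2 ratio of A to B.

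- SE = √(0.798 × 0.202/50 + 0.788 × 0.212/100) = 0.0700, and 1.96 × SE = 13.7 points.
- A − B with no reclassification: 1.0 (95% CI −12.7 to 14.7).
- k = 1: −1.0 (−15.0 to 13.0).
- k = 3: −5.0 (−19.6 to 9.6).

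One patient is enough to change the sign of this illustrative estimate, but the interval is about 27 points wide throughout.

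**5. Extension clause.** Item 2 applies only beyond the scheduled end of treatment. Protocol 2.1.4 describes A as a 20- to 24-month regimen: 20 × 365.25/12/7 = 87.0 weeks and 24 × 365.25/12/7 = 104.4 weeks. The Week 76 window normally closes at Week 82, before either. Only a COVID-extended window (76 + 14 = Week 90) could pass the shorter figure. The list in SAP 7.1.4 of events after Week 76 has no extension criterion.

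**6. After Week 76.** A has 87.0 − 76 = 11.0 to 104.4 − 76 = 28.4 weeks of scheduled treatment left. B and C (at most 48 weeks with smear extension) and D (at most 36) have finished, apart from make-up days. A single-drug replacement during that time can arise only on A, and neither document says whether it counts as starting treatment.

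**The case against.** The strongest reply is that the omission catches very little. Moving a patient from A to the 2016 short regimen is item 1. The December 2018 guidance gave prominence to bedaquiline and linezolid, and starting either is item 5 or 7. Replacing kanamycin with amikacin is a single-drug replacement. All of these are scored alike in both documents. Protocol 2.1.4 also says patients already on A will continue on it. What remains is a multi-drug, guideline-driven change outside items 1, 5 and 7, and nothing in the documents shows that any were expected. This stands: it limits the reach of the point but does not explain why the clause is absent. The visible rows of the SAP version history (1.5 to 6.0) record no decision to withdraw it.

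The reply also notes that the A comparisons are secondary, framed as estimation, and imprecise. That stands too. SAP 8.3 tabulates Week 132 culture status by arm regardless of treatment changes, but it calculates no contrast with A.

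A reader might infer three stronger things that the documents do not support.

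- **That the SAP newly counts any drug started on A after Week 76.** The wording is identical in Protocol 11.2.2. It refers to MDR-TB treatment, not to any drug, and SAP 3.2 separately treats starting a single drug as insubstantial, with listed exceptions. This is an unclear rule, not a SAP omission.
- **That local intensive-phase extensions on A would be scored as failures.** SAP 1.5 leaves A's transition to local policy, and step 5 shows little room for any effect on scoring.
- **That A alone lost an allowance.** SAP item 4 also lacks the protocol's footnote on changes from kanamycin to amikacin, a separate discrepancy that concerns other regimens.

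**Conclusion.** The point holds for the guideline exemption. Protocol 11.2.1 and SAP 3.2 classify one type of Regimen A patient differently, the SAP governs, and the difference runs in one direction: against A in the B-A, C-A and D-A Week 132 estimates. Each patient affected moves A by at least 2 points if A has at most 50 patients. How many there are is unknown, so this is a sensitivity and not a measured bias; it could be zero.

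The conclusion assumes that the analysis follows the SAP's wording, and that the second exemption qualifies item 4 only and does not override items 1, 5 or 7. The omission does not touch the primary B versus C comparison at Week 76, which does not use Regimen A. Nor would it be right to say that comparability with Stage 1 depends on this clause alone: Protocol 11.2.1 already treats reinfections and missing cultures differently in the two stages.

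**What to change.** 1. In SAP 3.2 item 4, restore the second exemption: a change is not unfavourable "for patients allocated to Regimen A when the change is as a result of changes in local guidelines" and the reason is unrelated to the patient. If the omission was deliberate, say so and give the reason.
2. In the SAP 3.2 paragraph on extensions, restore "or the locally-used WHO 2011 long MDR-TB regimen for patients on Regimen A". This removes an ambiguity and should change little or nothing in the scoring. The cross-reference there to Figures 5 and 6 also needs correcting, since SAP 1.5 contains Figures 1 to 3.
3. In SAP 7.1.4, state that a single-drug replacement within ongoing allocated Regimen A after Week 76, other than one caught by items 5 or 7, does not count as starting MDR-TB treatment. Label this a clarification of wording shared with Protocol 11.2.2.
4. Do not add item 2 to the list of events after Week 76. That would newly penalise A for treatment extensions that neither document counts there.

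The cost is a few lines of SAP text and a review of at most about 50 records, in which someone must confirm from the recorded reason that a change was guideline-driven. SAP v6.0 (September 2022) postdates the Week 76 primary analysis, so the amendment should be described as restoring the protocol's rule, and the three A comparisons should be shown with and without it.

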This document describes and substantiates the statistical principles and methods used for the analysis of data from Stage 2 of the STREAM trial. This document is designed to support the STREAM protocol but this Statistical Analysis Plan (SAP) supersedes the SAP as written in the protocol. Every care was taken in the drafting of this SAP, but corrections or amendments may be necessary. A pre-final version (v1.0) of this SAP was signed off before first patient first visit. The final version of the SAP will be signed off before database lock for the primary Week 76 Stage 2 analysis.

The STREAM trial consists of two stages. Stage 1 involves the comparison of two treatment regimens: Regimen A and Regimen B. Stage 2 involves two additional regimens, Regimen C and Regimen D, and makes the comparison between Regimen B and Regimen C for the analysis of the primary endpoint. All treatment regimens are described in detail in the STREAM protocol, Section 2.1.3. Stage 1 and Stage 2 of the STREAM trial each have separate SAPs listed below. Each SAP has differences, but the fundamental statistical principles will be consistent across all SAPs.

Document	Description
Stage 1 SAP	All analyses relating to stage 1
Core Stage 2 SAP	Core analyses for stage 2
Extensive Stage 2 SAP	Expanded analyses for stage 2 supporting CSR

Compliance:

The trial will be conducted in accordance with the ethical principles that have their origin in the Declaration of Helsinki, in accordance with the principles of Good Clinical Practice (GCP) as laid down by the ICH topic E6 (Note for Guidance on GCP), and the applicable regulatory requirements in the participating countries.

Sponsor:

Vital Strategies, f/k/a The International Union Against Tuberculosis and Lung Disease, Inc. [name]

Tel (main): [contact] [contact]

Email: [contact]

Funders:

The United States Agency for International Development (USAID) UK Medical Research Council (MRC) / Department for International Development (DFID) Janssen Research & Development, LLP (Stage 2 only)

Main Contacts:

Co-Chief Investigator

[name] MRC Clinical Trials Unit at UCL Institute of Clinical Trials and Methodology [name]

[contact] [contact] Email: [contact]

Co-Chief Investigator

[name] MRC Clinical Trials Unit at UCL Institute of Clinical Trials and Methodology [name]

[contact] [contact] Email: [contact]

CONTENTS

1	Trial overview	8

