3.1.1 Extension of visit window due to the COVID-19 pandemic

The end dates of the Week 76 window will be extended for any Stage 2 patients whose Week 76 appointment is scheduled to occur during the COVID-19 pandemic and did not occur due to restrictions on movement, unacceptable risk of exposure to COVID-19 in connection with the scheduled visit, or any other reason related to the pandemic. For those patients, the Week 76 sputum samples must be taken in a window beginning six weeks prior to the scheduled visit date and ending within the Week 84 visit window i.e. within 14 weeks of the scheduled Week 76 visit date.

3.2 **Primary efficacy outcome**

The primary efficacy outcome measure is the proportion of patients with a favourable outcome (as defined below) at Week 76.

Only data from events occurring before the end of the Week 76 window will be included in the primary analysis of the primary efficacy outcome.

Culture results obtained using acidified Ogawa (Kudoh medium) will be used in the primary analysis, unless missing, when results from Löwenstein-Jensen (LJ) media will be used.

A positive culture is defined as at least one colony and a negative culture is defined as absence of growth (no colonies).

Favourable

A patient's outcome will be classified as **favourable** if their last two culture results are negative unless they have previously been classified as unfavourable. These two cultures must be taken on separate visits (on different days); the latest of which being within the Week 76 window.

Patients that don't have a culture result within the Week 76 window because they were unable to produce sputum or their sample was contaminated, will be classified as favourable if their last two cultures before the Week 76 window are negative and they have not previously been classified as unfavourable; such patients will be identified separately in tables.

Participants with no sputum sample available at Week 76 due to Covid-19 restrictions who are not otherwise classified as unfavourable will be considered unfavourable. Sensitivity analyses will reclassify these participants as i) non-assessable and excluded from the primary efficacy analysis, and ii) favourable if they meet the definition of favourable above, with the latest of the 2 negative culture results being within the Week 68 window, and unfavourable otherwise.

Unfavourable

A patient's outcome will be classified as **unfavourable** in Stage 2 if:

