Failure to complete a protocol adherent course of allocated treatment	Treatment policy: same as above	Principal Stratum: population is the subgroup of participants who would adhere to treatment, whichever treatment they are allocated
Reinfection	Composite strategy: same as above	Composite strategy: same as above
Death	Composite strategy: same as above	Composite strategy: same as above

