6.2 Tabulation of primary endpoint classification

Since the primary endpoint is a composite of various components, the actual reason (component) for outcome will also be tabulated by treatment arm. Patients will be classified by the first event that made the patient unfavourable (see section 3.2) and further subclassified by whether their outcome is deemed to be bacteriologically related or not, based on a review of all data up to the time that the outcome occurred (see Section 6.2.1).

6.3 **Subgroup analyses**

This primary efficacy analysis will be repeated (in both mITT and PP analysis populations) in subgroups according to the following baseline characteristics:

- HIV infection status
- baseline drug resistance patterns (i.e. resistance to pyrazinamide and isoniazid)
- albumin levels (by severity grade)
- BMI (<16.0 kg/m², 16.0-18.4 kg/m², 18.5-24.9 kg/m², >25 kg/m²)
- cavitation (presence, absence)
- study centre/country
- age (<25, 25-<45, ≥45)

- sex
- Smoking history (current, ex, never)
- Smear grade
- Weight band (<33kg, 33-50kg, >50kg)
- Race.

6.4 **Sensitivity analyses**

The primary efficacy analysis will be repeated:

- A. Unadjusted for any covariates except randomisation protocol.
- B. Adjusted for randomisation stratification factors HIV status and centre. Small strata with fewer than 10 patients will be combined within geographical regions within country.
- C. Adjusted for randomisation stratification factors and any additional important covariate such as cavitation at baseline, baseline bacillary load or adherence.
- D. Ignoring substitutions of levofloxacin for moxifloxicin and vice versa when counting the number of drug substitutions within the definition of unfavourable outcome.
- E. Ignoring starting linezolid alone as a criterion for an unfavourable outcome.
- F. Reclassifying any participants with reinfection (based on genotype or DST) as "non-assessable" rather than unfavourable.
- G. Reclassifying any participants who died as a result of trauma (as adjudicated by independent review) as "non-assessable" rather than unfavourable.
- H. Reclassifying any participants with missing Week 76 culture results because of COVID-19 as "non-assessable" rather than unfavourable.
- Reclassifying any participants with missing Week 76 culture results because of COVID-19 as favourable if they meet the definition of favourable, with the latest of the 2 negative culture results being within the Week 68 window, unfavourable otherwise.

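### SAP 3.2 omits the reinfection criterion that the protocol, the SAP's own estimand table and sensitivity analysis F all rely on, so a small class of reinfected patients would be scored favourable

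*SAP*

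**What the plan says.** **Protocol 11.2.1, Unfavourable.** The list has eleven items. Item 11, for Stage 2 only, reads: "The failure or recurrence specimen at or before the Week 76 window was a different strain to their randomisation specimen, i.e. re-infection". For Stage 1 the same section treats reinfections as not assessable, so the two stages differ on this point.

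**SAP 3.2, Unfavourable.** The list has ten items, numbered without a break. The tenth is "They do not have a culture result within the Week 76 window". Two others bear on reinfection whatever the strain: item 3 (restarting MDR-TB treatment after the scheduled end of treatment and before 76 weeks) and item 9, "At least one of their last two culture results, from specimens taken on separate occasions, is positive". The favourable rule is met "if their last two culture results are negative unless they have previously been classified as unfavourable", provided that the two cultures come from separate visits and the later one falls in the Week 76 window. Strain plays no part in either rule. SAP 3.2 applies its definitions to every regimen and to the mITT, PP and mPP populations.

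**SAP 3.3.** Component (c) takes the endpoint from Section 3.2. The intercurrent-event table gives reinfection the entry "Composite strategy: same as above" under both co-primary estimands. The table explains that strategy as one in which the event is part of the endpoint's definition and the patient is unfavourable.

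**SAP 6.4, analysis F.** "Reclassifying any participants with reinfection (based on genotype or DST") moves such patients to non-assessable from a presumed unfavourable status.

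**SAP General Information.** It states that "this Statistical Analysis Plan (SAP) supersedes the SAP as written in the protocol".

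**The concern.** The composite strategy in 3.3 works only if the endpoint it points to contains the event. Section 3.2 does not. A programmer who codes 3.2 and one who codes the 3.3 table could classify the same patient differently, and the primary analysis could then estimate something other than the declared estimand.

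Analysis F is affected too. For a patient already scored favourable under 3.2, F would move a favourable patient, not an unfavourable one, to non-assessable. That is not the contrast F describes.

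The gap also reaches analyses that reuse 3.2 or the Week 76 status:
- the tabulation of reasons in 6.2, which has no reinfection category;
- time to unfavourable outcome in 7.1.2;
- Week 132 status in 7.1.4, which inherits Week 76 status.

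This is the primary endpoint of an open-label non-inferiority trial, so the rule should not be left to be chosen when such a patient turns up in the data.

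**Working it through.** **1. Text check.** The two lists, side by side:

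| Source | Reinfection by the Week 76 window |
|---|---|
| Protocol 11.2.1, item 11 | Unfavourable |
| SAP 3.2, items 1 to 10 | Not mentioned |
| SAP 3.3 table, both estimands | Composite, so unfavourable |
| SAP 6.4 F | Presumed unfavourable, then set to non-assessable |

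**2. Which patients are affected under SAP 3.2 alone.**
- (a) Reinfected and put on MDR-TB treatment before 76 weeks: unfavourable by item 1 or item 3. No conflict.
- (b) Reinfected with a positive among the last two cultures: unfavourable by item 9. No conflict.
- (c) Reinfected after treatment, for example with different-strain positives at Weeks 52 and 60, no new treatment, and negatives at Weeks 68 and 76: none of items 1 to 10 applies and the favourable rule is met, so the patient is **favourable**. Protocol item 11 and SAP 3.3 make this patient **unfavourable**.
- (d) A single different-strain positive followed by two negatives: SAP 5.5 does not treat this as the end of culture-negative status, so it may not be a failure or recurrence specimen at all. This case is unclear, which is why (c) uses two positives.

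Case (c) is possible under the plan: protocol section 9 provides for a decision not to retreat.

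**3. The plan's sample size, for scale.** Inputs from SAP 2.1: 80% favourable on B, 82% on C, margin 10 points, one-sided 2.5%, 80% power.
- Unpooled variance: n = (1.960 + 0.842)² × (0.80×0.20 + 0.82×0.18) / (0.10 + 0.02)² = 7.849 × 0.3076 / 0.0144 = 167.7, so 168 per arm.
- Restricted null variance (Farrington-Manning): 171.1, so 172 per arm, which is the plan's figure.
- Exclusions of 14%: 344 / 0.86 = 400 in total, also the plan's figure.

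The point raised here does not change any of these.

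**4. Effect per patient.** 1/200 = 0.50 points and 1/172 = 0.58 points in one arm.

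**5. Effect on the confidence bound.** Simple unstratified Wald interval at the planning rates with 172 per arm; the plan's own analysis is stratified, so this shows scale only. Let k be the number of Regimen C patients moved from favourable to unfavourable:

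upper bound of B − C = (0.80 − pC) + 1.96 × √[(0.80×0.20 + pC(1 − pC)) / 172], with pC = 0.82 − k/172.

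| k | B − C (points) | Upper 95% bound (points) |
|---|---|---|
| 0 | −2.00 | 6.29 |
| 1 | −1.42 | 6.92 |
| 2 | −0.84 | 7.55 |

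Moving Regimen B patients instead shifts the bound the other way. The range of 0 to 2 is an assumption; the documents give no number of reinfections.

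**The case against.** The strongest reply is that the SAP has not abandoned the rule. Sections 3.3 and 6.4 F both show the intended classification, and nothing in the SAP says that reinfection is favourable. That stands. A reader might infer from the shorter list that the SAP reverses the protocol, but the documents do not support this. The part of the SAP version history that is shown, from v1.5 on, records no such decision, and an omission is the likelier explanation.

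A second reply is that protocol item 11 only clarifies. Items 1 to 10 ignore strain, and item 11 tells the reader that Stage 2, unlike Stage 1, does not excuse reinfection. In support, an unretreated same-strain recurrence that ends in two negatives is favourable under items 1 to 10, so a stand-alone item 11 treats a different-strain recurrence more harshly. This oddity is real. It does not remove the conflict, because the 3.3 table lists reinfection itself as an event that makes the patient unfavourable. If clarification was all that was meant, 3.3 needs to say so.

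Third, the supersession sentence could be read as covering only the protocol's preliminary analysis plan (11.6), leaving the outcome definition in 11.2.1 in force. That is arguable. A reader might infer that supersession has cancelled item 11, but the wording does not settle this either way. The uncertainty is itself a reason to put the item in SAP 3.2.

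Fourth, few patients can be affected, and patients in opposite arms offset each other. This stands and limits the size of the point.

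**Conclusion.** The point holds as an internal contradiction. The section named as the primary endpoint lacks a criterion that the estimand table and analysis F need. Applied as written, it scores case (c) as favourable, against both the protocol and the SAP's own estimand.

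Its likely size is very small. With an assumed 0 to 2 patients, the shift is 0 to about 1.2 points in one arm. At the planning rates, two such patients in Regimen C leave the upper bound near 7.6 points, inside the 10-point margin. A reader might infer that the non-inferiority conclusion is at risk; the documents give no count that would support this. A reader might also infer that any different-strain positive culture would be wrongly scored. That goes too far, because items 1, 3 and 9 probably catch most reinfections and SAP 5.5 leaves the isolated positive unclear.

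The case for correcting it is that the primary endpoint should have one rule and that the correction is cheap.

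**What to change.** Add an item 11 to the unfavourable list in SAP 3.2: a failure or recurrence specimen at or before the Week 76 window whose strain differs from that of the randomisation specimen (reinfection) makes the outcome unfavourable.

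Copying the protocol item alone would not give one rule, because the protocol speaks of strain while analysis F accepts genotype or DST. So also write a single definition of reinfection, stating whether it rests on strain typing only or also on a change in DST, and refer to it from 3.2, 3.3 and 6.4 F. The same definition should say whether an isolated positive followed by two negatives counts as a recurrence specimen, in line with SAP 5.5. Add reinfection as a reason in the 6.2 tabulation.

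The cost is a few lines of SAP text and one derivation step. Protocol 8.7 already has recurrence strains fingerprinted and DST-tested against the first isolate, so no new data are needed, and the sample size does not change.
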